## 1 ABBREVIATIONS

AASLD	American Association for the Study of Liver Disease
AE	adverse event
ALF	acute liver failure
ALF-MBT	Acute Liver Failure  C-Methacetin Breath Test
ALFSG	Acute Liver Failure Study Group
ALFSG-PI	ALFSG Prognostic Index
ALI	acute liver injury
ALT	alanine transaminase
APACHE II	Acute Physiology and Chronic Health Evaluation II
APAP	acetaminophen (acetyl-para-aminophenol)
ARDS	Acute Respiratory Distress Syndrome
AST	aspartate aminotransferase
AUROC	area under the ROC curve
CPDR	cumulative percentage of  C dose recovered over time
CRF	case report form
CTCAE	Common Terminology Criteria for Adverse Events
CVP	central venous pressure
DCR	Data Clarification Request
DCU	Data Coordination Unit
DIC	disseminated intravascular coagulation
DHHS	Department of Health and Human Services
DOB	delta over baseline
DSMB	Data Safety Monitoring Board
EC	Ethics Committee
eCRF	electronic case report form
ET	endotracheal
FDA	U.S. Food and Drug Administration
FEV 1	forced expiratory volume in one second
FiO 2	fraction inspiratory oxygen
GCP	Good Clinical Practice
GI	gastro-intestinal
HE	hepatic encephalopathy
ICH/GCP	International Conference on Harmonization Good Clinical Practice Guidelines

ICU	Intensive Care Unit
IDE	Investigational Device Exemption
INR	International Normalized Ratio
IRB	Institutional Review Board
KCC	King's College Criteria
LAR	legally authorized representative
LT	liver transplant
MAP	mean arterial pressure
MBT	 C-Methacetin Breath Test
MCS	molecular correlation spectrometry
MedDRA	Medical Dictionary for Regulatory Activities
MELD	Model for End-Stage Liver Disease
MOP	Manual of Procedures
MSM	medical safety monitor
NAC	n-acetyl cysteine
NIDDK	National Institute of Diabetes and Digestive and Kidney Diseases
NIH	National Institutes of Health
PaO 2	partial arterial oxygen
PDR	percentage of dose recovered over time
PDR Peak	the maximum value of PDRs
PEEP	positive end expiratory pressure
PI	principal investigator
RBC	red blood cell
ROC	receiver operating characteristic
RRT	renal replacement therapy
SAE	serious adverse event
SAR	suspected adverse reaction
ScvO 2	central venous oxygen saturation
SDCC/MUSC	Statistical Data Coordinating Center at the Medical University of South Carolina
SOFA	Sequential Organ Failure Assessment
SS	spontaneous survivors
SSL	secure socket layer
WBC	white blood cells

Study Population	Approximately 200 male and female patients, aged 18 to 80 years (have not reached their 81 st birthday) with severe acute liver injury that is not related to acetaminophen overdose or acute liver failure present at the time of enrollment into the ALFSG Registry will participate.
Study Design	
This is a multicenter, open label, non-randomized study to determine the value of BreathID® C-Methacetin Breath Test System (MBT) in predicting the outcome of patients diagnosed with severe acute liver injury that is not related to acetaminophen overdose and acute liver failure who meet inclusion/exclusion criteria.
 
Informed consent will be obtained from the patient and/or patient’s legally authorized representative (LAR) or family member as defined in 21CFR50.3(m). All patients will receive medical care for severe acute liver injury or acute liver failure according to the institution’s standards of care.
 
Up to 200 evaluable patients will be consecutively enrolled. The MBT (also referred to as “Breath Test”) will be performed up to five times during the study period on all enrolled patients. An evaluable patient is one who has completed one or more Breath Tests measured for a minimum of 30 (and ideally 60) minutes after administration of the C-Methacetin solution (also referred to as “test substrate”). The first Breath Test will be performed upon admission into the study (Day 1) and repeated on Days 2, 3, 5 and 7, as close to the same time of day as possible, provided no contra-indications are present.
 
If a patient who is enrolled into the ALFSG-MBT Trial with ALI converts to ALF, breath test collection will continue until the maximum of five Breath Tests have been performed. Once the ALI patient has been enrolled into the ALFSG Registry with ALF, subsequent Breath Tests should be performed as close to the same time of day as the previous Breath Tests provided no contra-indications are present. During the initial consent process, the enrolled ALI patient should indicate consent to continue participation into the ALFSG-MBT study should the disease progress to ALF.
 
If an enrolled ALI or ALF patient receives a liver transplant, is discharged /transferred from the hospital or dies prior to Day 7, additional Breath Tests will not be performed.
 
Subjects will be contacted to determine Day 21 spontaneous survival, transplantation and occurrence of serious adverse events since the last Breath Test.
 
Only trained study personnel will perform the breath test procedure and administer the test substrate. Site principal investigators (PIs) and clinical staff will be blinded to the results of the MBT so that there cannot be any reliance on the MBT for clinical decision-making.


Inclusion Criteria	
 
1. Adult men or women (18-80 years of age)
 
2. Severe acute liver injury (ALI), defined as the development of coagulopathy (International normalized ratio [INR] <math>\geq 2.0</math>) and not related to acetaminophen overdose, with no evidence of hepatic encephalopathy (HE); these patients may provide consent themselves.
 
3. Acute liver failure, defined as the development of coagulopathy (INR <math>\geq 1.5</math>) with HE
 
4. Duration of illness <26 weeks
 
5. Enrolled into the ALFSG Registry
 
6. Written informed consent from the patient or patient's legally authorized representative or family member as defined in 21CFR50.3(m)
 

Exclusion Criteria	
 
1. Evidence of pre-existing chronic liver disease
 
2. Pre-existing New York Heart Association stage III/IV heart failure
 
3. Evidence of pre-existing chronic renal failure requiring hemodialysis
 
4. Chronic hemodialysis prior to hospital admission
 
5. Evidence of cirrhosis (unless clinically acute Wilson disease or autoimmune non-APAP or ALF)
 
6. Severe obstructive lung disease (<math>FEV_1 < 50\%</math> of predicted on previous spirometry)
 
7. Severe shock, defined as MAP <70 mmHg despite >15 <math>\mu\text{g}/\text{kg}/\text{min}</math> dopamine, >0.1 <math>\mu\text{g}/\text{kg}/\text{min}</math> epinephrine, or >0.1 norepinephrine <math>\mu\text{g}/\text{kg}/\text{min}</math>
 
8. Extensive small bowel resection (>50 cm)
 
9. Any evidence of upper GI bleeding at enrollment requiring intervention (endoscopy or RBC transfusion specifically for upper GI bleeding)
 
10. Liver transplantation prior to enrollment (Note: Listing for LT does not preclude participation in the trial.)
 
11. Pregnancy or breastfeeding women (Note: Pregnancy related non-APAP ALI or ALF may be considered for entry following the delivery of the baby and assuming the mother does not wish to breastfeed or collect breast milk during the study period.)
 
12. Allergic to acetaminophen (such as Tylenol® or any other acetaminophen-containing medications)
 
13. Participation in other clinical studies evaluating other experimental treatments or procedures. (Note: Participation in observatory studies is not an exclusion.)
 
14. Patients in whom enteral drugs or fluids are contra-indicated or the patient either does not have an appropriately placed naso-
 


Exclusion Criteria Continued
	
enteric/orogastric tube in situ or cannot tolerate taking the drug preparation orally (200 ml)
 
15. Budd-Chiari Syndrome
 
16. Non-APAP ALI or ALF caused by malignancy
 
17. Moderate and severe ARDS, as defined by Berlin Criteria (see ALFSG-MBT Manual of Procedures (MOP))
 
18. Subjects who have received amiodarone in the 30 days prior to study enrollment
 
19. Consumption of any food or beverage that contains caffeine in the 24 hours prior to enrollment
 
20. Consumption of any of the following drugs that may interfere with the metabolism of C-Methacetin in the 48 hours prior to study enrollment including: allopurinol, carbamazepine, cimetidine, ciprofloxacin, daidzein, disulfiram, Echinacea, enoxacin, fluvoxamine, methoxsalen, mexilitene, montelukast, norfloxacin, phenylpropanolamine, phenytoin, propafenone, rifampin, terbinafine, ticlodipine, thiabendazole, verapamil, zileuton or oral contraceptives
 
21. Consumption of alcohol in the 24 hours prior to enrollment
 
22. Smoking cigarettes in the 8 hours prior to enrollment


Study Procedures
	
The MBT requires administration of an oral dose of C-Methacetin solution, followed by retrieval of expired CO2 over a period of one hour following the test substrate administration, representing first pass kinetics and the ability of the liver to withdraw and metabolize C-Methacetin, yielding the product, CO2.
 
Subjects will have up to five Breath Tests performed once enrolled into the trial and all requirements for the administration of the test substrate have been met. Subjects will be fasting for a minimum of 6 hours from solid food or a minimum of 4 hours from naso-enteric/orogastric tube feeding and tested, in most instances, in the morning hours. The test substrate may be administered in 200 ml of water by mouth or by naso-enteric/orogastric tube.
 
Breath is collected automatically for a total of 75 minutes (up to 15 minutes for baseline measurement and 60 minutes following enteral administration of C-Methacetin solution) using the BreathID® MCS device at the subject's bedside. Exhaled breath is collected via a nasal retrieval cannula or via connection of the BreathID® MCS device to the endotracheal tube in intubated patients. The BreathID® MCS device will record data over the 75 minute interval and then the cannula or ET tube connection is removed.
 
During the study hour, all other care may be administered to the patient, including renal replacement therapy, other food intake as necessary; however, it is preferred that the test substrate and Breath Test are not


Study Procedures Continued
	
administered during dialysis treatments and subjects remain fasting for the duration of the breath test collection.
 
Consumption of the following drugs that may interfere with (compete with or induce) the metabolism of C-Methacetin will be recorded on the case report forms and include the following:
 
 
a. HMG-CoA reductase (Statin) drugs in the 30 days prior to study enrollment;
 
b. Acyclovir and famotidine taken in the 48 hours prior to study enrollment; and
 
c. Any of the following taken during the study period: allopurinol, carbamazepine, cimetidine, ciprofloxacin, daidzein, disulfiram, Echinacea, enoxacin, fluvoxamine, methoxsalen, mexilitene, montelukast, norfloxacin, phenylpropanolamine, phenytoin, propafenone, rifampin, terbinafine, ticlodipine, thiabendazole, verapamil, zileuton or oral contraceptives.
 

Safety Evaluations
	
This is not a therapy trial; however, the safety of administration of C-Methacetin solution in this setting will be evaluated. Safety assessments will be performed by assessing for acetaminophen levels and levels of acetaminophen-Cys adducts, by collecting daily serum samples for adduct and APAP testing in the laboratory of [name], University of Arkansas for Medical Sciences, Little Rock, AR, on the first 20 evaluable ALF patients.

Safety Analysis
	
The detection of serum APAP-Cys adducts in those ALF patients not thought secondary to APAP toxicity will be considered significant if a value > 1.0 nmol/L is determined. Likewise, the detection of any level serum APAP in these patients will also be considered significant. An increase of significance in the adduct level in APAP cases or in serial serum APAP levels will also require adjudication as a possible indicator of an additional adverse effect of C-Methacetin administration. In addition, standard laboratory parameters including serum electrolytes and Liver biochemistries will be measured in all subjects through a maximum of 7 days (See Schedule of Assessments, Section 8.5).

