### 4.2.3 Safety Endpoints

The administration of Methacetin (75mg/dose) results in the generation of acetaminophen (75mg/dose), and therefore presents a modest safety concern in patients with ALF, particularly in those with APAP overdose. Use of NAC in patients admitted with APAP overdose or non-APAP ALF should obviate minor adverse effect potential of this small dose. In a retrospective study, sera from ALF patients who were given the C-Methacetin MBT at King's College were assayed for presence of acetaminophen adducts. Participants of this study received MBT daily up to 7 days. No *de novo* appearance of adducts was observed for non-APAP subjects, nor was there an increase in adduct levels in acetaminophen toxicity subjects.

To confirm the safety profile of the MBT, a prospective safety sub-study is planned for this protocol as outlined in Section 10.1. This safety sub-study will include determining APAP and APAP-adduct concentrations in sera from study participants with ALF immediately prior to each administration of the C-Methacetin solution. A positive safety endpoint is defined as:

1. the absence of decline in APAP or APAP-adduct concentration between two consecutive determinations for patients with ALF due to APAP overdose;
2. presence of a significant (toxic quantity,  $\geq 1 \mu\text{mol/L}$ ) APAP-adducts in patients with non-APAP ALF;
3. adjudicated cases where APAP (non-adduct, parent compound) is detected in the serum of a patient with non-APAP ALF. It should be noted that in some instances, APAP appears to be detected in patients with non-APAP ALF if the total bilirubin is  $\geq 10 \text{ mg/dl}$ ; these are considered false-positive due to the cross-reactivity between APAP reactants and bilirubin in some colorimetric APAP assays (Polson, et al.). Such cases of detectable APAP in patients with non-APAP ALF will be adjudicated on an individual basis by the study's appointed

independent Medical Safety Monitor to determine the likelihood of Methacetin toxicity. Results of adduct testing will initially be reviewed internally and forwarded in real time to the MSM for review. These data will then be reported in summary fashion to the DSMB.

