#### **8.3 Performance of the APAP Adduct Assays and APAP Concentration Assays**

Serum for acetaminophen (APAP) and APAP-adduct levels will be collected with routine morning labs on each day from Day 2-7, as well as Day 1 as a baseline value, from the first 20 ALF subjects enrolled. Serum samples will be reserved for the sole purpose of determining whether APAP or APAP-adducts accumulate during repeated administrations of the C-Methacetin solution in patients with ALF. The collected samples will be shipped to and analyzed by [name] at the University of Arkansas.

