## 8.5 Schedule of Assessments

	Screening/ Subject Enrollment	Day 1	Day 2	Day 3	Day 5	Day 7	Day 21
Demographics	X						
Medical History	X						
Confirm Eligibility Criteria ^	X						
Prior Medications	X						
Concomitant Medications		X	X	X	X	X	
Grade of HE	X	X	X	X	X	X	
Labs (lactate, bicarbonate, INR, total bilirubin, phosphate, Creatinine, WBC, Platelet count, ammonia-arterial or venous (if clinically indicated))		X	X	X	X	X	
RRT (record time/tx prior to MBT)		X	X	X	X	X	
MBT		X	X	X	X	X	
Serum for APAP and APAP-adduct levels*		X	X	X	X	X	
AE Reporting		X	X	X	X	X	(SAEs only)
End of Study							X
Collection of data for MELD, KCC, and ALFSG- PI	X	X	X	X	X	X	

\* Only in the first 20 consecutive ALF subjects enrolled

^ In women of child-bearing potential; Urine pregnancy test or blood human chorionic gonadotropin (hCG) is acceptable.

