## **10 SAFETY AND ADVERSE EVENTS**

### **10.1 Safety Sub-study**

The safety of the MBT has been demonstrated in several clinical applications. However, the repeated administration of the test substrate, which represents the equivalent of 75 mg of APAP per administration, will be closely monitored to ensure that this small dose of APAP will not result in additional liver injury (particularly in the presence of NAC). The results of the Retrospective Safety Study were examined before enrollment in the prognosis study began, as outlined in Section 4.2.3 of this protocol. A second, prospective safety study will be performed and sera collected from the first 20 ALF subjects enrolled into the ALF-MBT Trial as described herein, in whom we propose to administer MBT on Day 2, 3, 5, and 7 unless the subject is discharged/transferred, transplanted or dies. Serum for acetaminophen (APAP) and APAP-adduct levels will be collected with routine AM labs on each day from Day 2-7, as well as Day 1 as a baseline value. Serum samples will be reserved for the sole purpose of determining APAP or APAP-adducts levels in patients with ALF during repeated administrations of the C-Methacetin solution and will be performed by [name] at the University of Arkansas for Medical Sciences, Little Rock, AR.

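### The adduct level that counts as significant in non-APAP ALF is > 1.0 nmol/L in the synopsis but ≥ 1 µmol/L in Section 4.2.3, a 1000-fold conflict

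*Combined protocol and SAP*

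**What the plan says.** The synopsis, under Safety Analysis, gives this rule for ALF not attributed to APAP: "The detection of serum APAP-Cys adducts in those ALF patients not thought secondary to APAP toxicity will be considered significant if a value" greater than "1.0 nmol/L is determined". The inequality is strict and the unit is nmol/L.

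Section 4.2.3 lists three forms of positive safety endpoint for the prospective sub-study. Item 2 is a significant level, glossed there as a toxic quantity and set at ≥ 1 µmol/L, of "APAP-adducts in patients with non-APAP ALF". The inequality is non-strict and the unit is µmol/L.

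On handling of results, Section 4.2.3 says: "Results of adduct testing will initially be reviewed internally and forwarded in real time to the MSM for review". It continues: "These data will then be reported in summary fashion to the DSMB".

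The sections on sampling give no adduct threshold:
- Section 8.3 says serum "will be collected with routine morning labs on each day from Day 2-7, as well as Day 1 as a baseline value".
- Section 10.1 says likewise that it "will be collected with routine AM labs on each day from Day 2-7", with Day 1 as baseline.
- Section 8.5 marks samples on Days 1, 2, 3, 5 and 7, with the footnote "Only in the first 20 consecutive ALF subjects enrolled".

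**The concern.** Both statements concern serum APAP adducts, in non-APAP ALF, in the same prospective sub-study. A threshold that classifies a safety result should have one value. With two, the same laboratory report can be called significant by a reader of the synopsis and not a positive endpoint by a reader of Section 4.2.3.

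The sub-study exists to check whether repeated 75 mg doses, each yielding an equivalent amount of APAP, cause further liver injury. Adduct appearance in non-APAP ALF is one of its three defined positive endpoints. If the threshold is settled only after results are seen, that endpoint is no longer pre-specified, and the number of positive cases given to the DSMB could depend on which page was used.

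**Working it through.** The documents derive no figure from these thresholds, so there is no stated calculation to reproduce. The check is a unit conversion and a comparison of the two rules.

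**Inputs**
- Synopsis, Safety Analysis: > 1.0 nmol/L, ALF not thought to be due to APAP.
- Section 4.2.3, item 2: ≥ 1 µmol/L, non-APAP ALF.
- Sub-study size: 20 ALF patients (synopsis and Sections 8.3, 8.5 and 10.1).

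**Ratio of thresholds**

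1 µmol/L = 1000 nmol/L, and 1000 nmol/L ÷ 1.0 nmol/L = 1000.

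**Classification under each rule**

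| Adduct level (nmol/L) | Synopsis: significant? | Section 4.2.3: positive endpoint? |
|---|---|---|
| 0.5 | no | no |
| 1.0 | no | no |
| 2 | yes | no |
| 50 | yes | no |
| 500 | yes | no |
| 999 | yes | no |
| 1000 | yes | yes |
| 2000 | yes | yes |

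The rules agree at or below 1.0 nmol/L and at or above 1000 nmol/L. They disagree everywhere between. The difference between > and ≥ is minor beside the unit conflict.

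**Number of results the definition applies to**

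The documents do not say how many of the first 20 ALF patients will be non-APAP cases. Call this number *k*, assumed to lie anywhere from 0 to 20.
- Five sampling days (Section 8.5): at most 5 × *k* results.
- Seven sampling days (Sections 8.3 and 10.1, daily on Days 1 to 7): at most 7 × *k* results.
- For *k* = 10: 5 × 10 = 50 to 7 × 10 = 70.
- For *k* = 20: 5 × 20 = 100 to 7 × 20 = 140.

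These counts are ceilings. They include the Day 1 baseline and assume that every patient gives every sample. They are the results to be classified, not the results in dispute.

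**Search for a reconciling statement**

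Sections 8.3, 8.5 and 10.1 contain no threshold and describe no tiers. A slip in the volume unit could explain the difference, since 1.0 nmol/mL × 1000 mL/L = 1000 nmol/L = 1 µmol/L. The documents neither confirm this nor show which value is intended.

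**The case against.** The strongest reply is that little depends on the threshold. Neither value feeds a stopping rule, a dosing rule or any analysis in Section 12. Section 4.2.3 sends adduct results to the Medical Safety Monitor with no threshold condition, so no result is hidden from review. The summary to the DSMB may consist of the adduct results themselves rather than a count of classified cases. All of this stands. It limits the consequence to labelling and counting, and an effect on the DSMB summary is possible rather than certain.

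A second reply is that the labels differ: the synopsis flags significance, while Section 4.2.3 defines an endpoint at a toxic quantity, so a low flag and a higher endpoint might both be meant. This does not hold up. Section 4.2.3 applies the word *significant* to its own threshold, and no two-level scheme is described anywhere. If one was intended, the protocol would still need to say so.

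A third reply is that the ceilings of 100 to 140 results are generous. That is fair. Item 1 of Section 4.2.3 provides for APAP-overdose patients in the same sub-study, and breath tests stop at discharge, transfer, transplant or death. Section 4.2.3 also reports no new adducts in non-APAP subjects in the retrospective study, though it gives no detection limit. The number of results in the disputed range may be zero.

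An error in reading a unit symbol from the PDF cannot be strictly excluded, but nothing in the text points to one.

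**Conclusion.** The contradiction is real and should be fixed. Two current passages give thresholds exactly 1000-fold apart for the same analyte, patients and sub-study, and nothing reconciles them. Results above 1.0 and below 1000 nmol/L are classified differently by the two texts.

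The reach is at most 20 patients. The factor of 1000 rests only on the printed values. The result counts rest on the assumed *k* and on complete sampling. How many results actually change label is unknown.

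Endpoint item 1 (APAP-overdose cases), the primary PDRPeak analysis, the sample size and the futility rule are untouched. This review takes no position on which threshold is right.

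**What to change.** Reconcile the synopsis (Safety Analysis) and Section 4.2.3, item 2, so that both carry the same threshold, unit and inequality, confirmed against the assay laboratory's specification. If two levels were intended, define both and say what each is used for. Apply the settled definition to every sub-study result, including any already classified.

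The cost is wording in two places. If classification has begun, it also means relabelling at most 100 to 140 results from at most 20 patients. No new samples, patients or procedures are needed.
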